## 8. SAFETY

### 8.1. COMPLIANCE

Patient compliance to visit attendance will be calculated using the following formula:

$$\frac{\text{Number of Visits Eligible to Attend} - \text{Number of Eligible Visits Not Attended}}{\text{Number of Visits Eligible to Attend}} \times 100$$

Where the number of visits eligible to attend will be derived for each patient from the time of infusion *i.e.* 5 years since infusion = 6 visits in long term follow-up at 2.5, 3, 3.5, 4, 4.5 and 5 years, etc. Repeat or unscheduled visits will not be included in the above calculation.

Visit compliance will be summarized using descriptive statistics, mean, median, standard deviation (SD), minimum, maximum and n separately by time since infusion ( $\leq 5$  yrs,  $> 5$  yrs/ $\leq 10$  yrs and  $> 10$  yrs) for 101, 102 and 202 and overall for PP population.

### 8.2. ADVERSE EVENTS

Throughout the long term follow-up, all serious adverse events (SAEs) and non-serious related adverse events (NSRAEs) observed by medical staff, or reported by the patient, will be evaluated by the investigator and noted in the adverse event section of the CRF.

SAEs and NSRAEs will be coded using the current Medical Dictionary for Regulatory Activities (MedDRA). SAEs and NSRAEs will be summarized separately for 101, 102 and 202 and overall by tabulating the frequency of reports for each unique event and by tabulating the number of patients experiencing one or more events. The denominator used for the calculation of percentages will be the number of patients in the Safety population for the respective long term follow-ups. SAEs and NSRAEs will be summarized by MedDRA system order class and preferred term. Separate data listings of all information relating to patient death, SAEs and NSRAEs will be provided.

SAEs are defined as events that have a seriousness category of death, life threatening, initial or prolonged hospitalization, disability, congenital anomaly or other medically important condition such as predominant integration site, positive RCR, malignancy or abnormal pregnancy outcome (*ie* recorded seriousness category of 1, 2, 3, 4, 5 or 6). AEs recorded as non-serious (7) will be defined as non-serious and will only be recorded if they are considered related to the gene transfer product. A related AE is defined as any

<Protocol: Janssen OZ1-HV1-101/102/202>

<INC code: 1003733>

<SAP Version: 3.0>

AE whose relationship to the gene transfer product is recorded as possible, probable or very likely (coded on CRF as 3, 4, or 5). Severe AEs are defined as any AE recorded in the 'severe' category (coded on CRF as 3). AEs leading to death are defined as any AE in the seriousness category of 'death' (coded on CRF as 1) and/or an outcome category of 'fatal' (coded on CRF as 5). NSRAEs are defined as adverse events (AEs) whose seriousness category is recorded as non-serious but are considered to have a possible, probable or very likely relationship to the gene transfer product.

If the severity or relationship of an SAE/AE is missing a worst case scenario will be assumed (*ie* the AE will be set to severe or very likely, respectively).

The following AE summary tables will be presented 101, 102, 202 and overall.

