5.2 Exclusion Criteria

All patients who were enrolled in the OTH/OZ1-INT-1 study and received the final cell product will be invited to participate in this long term follow-up study. After unblinding of the OTH/OZ1-INT-1 study, any patients in the placebo arm will be withdrawn from this protocol.

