### **3. STUDY DESIGN**

#### **3.1. OVERVIEW OF STUDY DESIGN**

The OZ1-HV1-101, OZ1-HV1-102 and OZ1-HV1-202 studies form the long term follow-up for OZ1. OZ1 comprises a Moloney Murine Leukemia Virus based retroviral vector (LNL6) containing a gene that encodes an anti-human immunodeficiency virus (HIV) ribozyme. It is a recommendation of the United States Food and Drug Administration (FDA) that all individuals receiving retroviral gene transfer products are followed for life.

Patients who participated in the Phase I study “A Marker Study of Therapeutically Transduced CD4+ Peripheral Blood Lymphocytes in HIV discordant twins” were asked to continue long term monitoring under the OZ1-HV1-101 protocol. Patients who participated in the Phase I study “A Phase I Trial of Autologous CD34+ Hematopoietic Progenitor Cells Transduced with an Anti-HIV Ribozyme” were to continued long term monitoring under the OZ1-HV1-102 protocol. Patients who participated in the Phase II study “A randomized Phase II, double blind, controlled trial to evaluate the safety and efficacy of autologous CD34+ hematopoietic progenitor cells transduced with placebo or an anti-HIV ribozyme (OZ1) in patients with HIV-1 infection” continue long term monitoring under the OZ1-HV1-202 protocol. Following completion and unblinding of the Phase II study, patients who were identified as having been enrolled in the placebo arm were subsequently discontinued from the long term follow-up study 202.

All patients in each protocol will be reviewed at 6 month intervals (+/- 6 weeks) until year 5 post infusion. Thereafter, all patients will be reviewed annually (+/- 12 weeks) on the anniversary of their infusion. Given the recommendation to follow patients for life, patients who withdraw from the study or have been lost to follow-up but return for assessments at a later time may be re-instated in their study. Additional unscheduled visits may be made if any clinical or biological findings require further investigation. A schedule detailing the timing of the follow-up visits and the procedures carried out at each visit is presented in Table 1.

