### **4.1. SAFETY POPULATION**

The Safety population will consist of any patient who was enrolled in either of the OZ1-HV1-101, OZ1-HV1-102 or OZ1-HV1-202 studies and continued into the respective long term follow-up protocol.

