### **4.2. PER-PROTOCOL POPULATION**

All patients who are eligible for inclusion in the Safety population and received OZ1 or LNL6 or combination OZ1/LNL6.

<Protocol: Janssen OZ1-HV1-101/102/202>

<INC code: 1003733>

<SAP Version: 3.0>

---

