## 5. OVERALL CONSIDERATIONS

All summary tables and data listings produced by INC will use the statistical package SAS (v9.2 or a more recent version).

In general, categorical data will be presented using counts and percentages, whilst continuous data will be presented using the descriptive statistics, mean, standard deviation (SD), median, minimum, maximum and number of patients with an observation (n). Minimum and maximum values will be quoted to the number of decimal places as recorded on the CRF; means, medians and SDs will be quoted to one further decimal place. Percentages will be rounded to one decimal place. Percentages smaller than 0.1 will be presented as <0.1. Percentages whose numerator is zero will be reported as zero.

All data recorded on the Case Report Form (CRF) and any derived data will be listed for all patients.

The Safety population will be used to present Adverse Event and death data. The PP population will be used to present all data .

Unless otherwise stated missing data will not be imputed. Patients who withdraw prematurely will have their data summarized at the last attended visit. Repeat assessments will not be summarized unless otherwise indicated but will be fully listed. Similarly, data collected at unscheduled visits will be listed only. Repeat and unscheduled visits will be identified on the data listings.

Where of interest, presentation of data will be pooled to reflect the target cell type, CD4 cells in OZ1-HV1-101 and CD34 cells in OZ1-HV1-102 and OZ1-HV1-202 in addition to presenting separately and overall.

<Protocol: Janssen OZ1-HV1-101/102/202>

<INC code: 1003733>

<SAP Version: 3.0>

---

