### 13. INDEX OF TABLES

Table Number	Table Description
14.1.1	Patient Disposition Including Reason for Discontinuation Summary Statistics: All Patients
14.1.2	Analysis Populations Summary Statistics: All Patients
14.1.3	Demographic Details Age, Gender and Race Summary Statistics: PP Population
14.1.4	Significant Medical History Time Since HIV-1 Infection Summary Statistics: PP Population
14.1.5	Treatment Details Summary Statistics: PP Population
14.1.5a	Treatment Details (Study 202 only) Summary Statistics: PP Population
14.1.6	Compliance Visit Attendance Summary Statistics: PP Population
14.2.1.1	OZ1 and LNL6 DNA PCR Marking Parameters (PBMC) Over Time: Actual Values Summary Statistics: PP Population
14.2.1.1a	OZ1 and LNL6 DNA PCR Marking Parameters (PBMC) Over Time: Actual Values (Study 202 only) Summary Statistics: PP Population
14.2.1.2	OZ1 and LNL6 DNA PCR Relationship of Marking Parameters (PBMC) with Calculated Dose, Age, Time on Study, Gender and Race Statistical Analysis: PP Population
14.2.1.2a	OZ1 and LNL6 DNA PCR Relationship of Marking Parameters (PBMC) with Calculated Dose, Age, Time on Study, Gender and Race (Study 202 only) Statistical Analysis: PP Population
14.3.1	Overall Summary of Adverse Events Summary Statistics: Safety Population
14.3.2	Serious Adverse Events By System Organ Class, Preferred Term, Severity and Relationship including Patient ID Summary Statistics: Safety Population
14.3.3	Serious and Non Serious Related Adverse Events By System Organ Class, Preferred Term, Outcome and Relationship including Patient ID Summary Statistics: Safety Population
14.3.4	Time Adjusted Serious Adverse Events By System Organ Class and Preferred Term Summary Statistics: Safety Population
14.3.5	Serious and Non-Serious Related Adverse Events Relationship Between Time on Study and Related Serious and Non Serious Adverse Events Summary Statistics: Safety Population

<Protocol: Janssen OZ1-HV1-101/102/202>

<INC code: 1003733>

<SAP Version: 3.0>

14.3.6	Patient Death By System Organ Class and Preferred Term, Including Patient ID Summary Statistics: Safety Population
14.4.1	Clinical History Experienced new or exacerbated pre-existing haematological disorders (including clinically significant laboratory abnormalities)? Summary Statistics: PP Population
14.4.2	Clinical History Had any new malignancies (including skin cancers)? Summary Statistics: PP Population

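### The adverse-event and death tables pool placebo and gene-transfer recipients in the 202, 102/202 and Overall columns, so those columns do not describe patients who received the product

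*SAP*

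**What the plan says.** - **Population.** SAP 4.1 begins "The Safety population will consist of any patient who was enrolled in either of the" three follow-up studies and adds only that the patient continued into long-term follow-up. It sets no condition on the product received. The PP population in 4.2 is the same set limited to patients who "received OZ1 or LNL6 or combination OZ1/LNL6", so its only extra criterion removes placebo recipients.
- **Placebo patients in 202.** Protocol 5.1 admits anyone who was given the final cell product in the Phase II trial, which includes the placebo arm. Protocol 5.2 says that after unblinding "any patients in the placebo arm will be withdrawn from this protocol". SAP 3.1 reports this as done: "patients who were identified as having been enrolled in the placebo arm were subsequently discontinued from the long term follow-up study 202". Discontinuation does not take a patient out of the Safety population.
- **Use.** SAP 5 assigns adverse-event and death data to the Safety population. SAP 8.2 says "The denominator used for the calculation of percentages will be the number of patients in the Safety population for the respective long term follow-ups". The index in Section 13 puts Tables 14.3.1 to 14.3.6 on that population.
- **Competing sentence.** SAP 5 also says "The PP population will be used to present all data", but no PP version of an adverse-event or death table is indexed or shelled.
- **Missing relationship.** SAP 8.2: "If the severity or relationship of an SAE/AE is missing a worst case scenario will be assumed". For relationship, this means the highest causality category.

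**The concern.** The protocol's objective is the long-term safety of the gene-transfer product. In the 202 and Overall columns of the adverse-event summaries, patients never exposed to the product, and followed only until unblinding, sit in the denominator, and their events sit in the numerator. A reader who takes these percentages as the experience of product recipients will be misled, usually towards a lower figure.

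The report would also be inconsistent with itself. The clinical-history tables (including new malignancies, Table 14.4.2) and the blood-count tables use PP. Malignancy is also an SAE under 8.2, so it is tabulated a second time on the Safety population. One key outcome would then rest on two different sets of patients.

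The index already adds 202-only versions on PP elsewhere, for example Table 14.1.5a: "Treatment Details (Study 202 only) Summary Statistics: PP Population". Marking has the same (14.2.1.1a and 14.2.1.2a). Adverse events do not.

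**Working it through.** The plan states no sample size or expected event figure, so there is nothing of its own to reproduce. The check first traces which columns are affected, then gives a range for the effect.

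**Columns affected**

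| Table | Columns | Effect |
|---|---|---|
| 14.3.1–14.3.3 | 202, Overall | Percentages and counts include placebo patients |
| 14.3.4 | 202, Overall | Placebo patient-years in the denominator; any placebo SAE rated related, or with relationship missing, in the numerator |
| 14.3.5 | 102/202, Overall | Patient counts include placebo; no percentages |
| 14.3.6 | 202, Overall | Placebo deaths counted; no percentages |

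The 101 and 102 columns are not affected.

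**Inputs**
- OZ1 recipients in 202: 37, taken as half of the 74 in Protocol 1.1. Full entry into follow-up is an assumption.
- Placebo entrants, k: not given. Taken as 5, 19 or 37.
- Patients from 101 plus 102, m: not given. Taken as 10 to 19.
- Time per OZ1 patient: 8 years, the protocol's 10-year minimum for ongoing patients less the 2 years that 8.2.4 subtracts. Applying it to every OZ1 patient is an assumption.
- Time per placebo patient, a: not given. Taken as 0.5 to 2 years.

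**Percentages in the 202 column.** For an event seen only in OZ1 recipients, the displayed value is 37/(37 + k) times the recipient-only value.

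| k | Factor | One patient reads | Recipient-only (1/37) |
|---|---|---|---|
| 5 | 37/42 = 0.88 | 1/42 = 2.38% | 2.70% |
| 19 | 37/56 = 0.66 | 1/56 = 1.79% | 2.70% |
| 37 | 37/74 = 0.50 | 1/74 = 1.35% | 2.70% |

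**Percentages in the Overall column.** For an event seen only in gene-transfer recipients, the factor is (37 + m)/(37 + m + k).
- k = 5: 47/52 = 0.90 (m = 10) to 56/61 = 0.92 (m = 19).
- k = 37: 47/84 = 0.56 (m = 10) to 56/93 = 0.60 (m = 19).

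**Event rate in 8.2.4, 202 column.** With no placebo SAE counted as related, the understatement is 1 − (37 × 8)/(37 × 8 + k × a), where 37 × 8 = 296.
- k = 5, a = 0.5: 1 − 296/298.5 = 0.8%
- k = 19, a = 1: 1 − 296/315 = 6.0%
- k = 37, a = 1: 1 − 296/333 = 11.1%
- k = 37, a = 2: 1 − 296/370 = 20.0%

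**Direction of the rate error.** Take k = 37 and a = 1, and let one placebo SAE count as related. With r related SAEs in OZ1 recipients, the pooled rate is too high when (r + 1)/333 > r/296. That is 296 > 37r, or r < 8. With r = 2, the table shows 3/333 = 0.90 per 100 patient-years, where the recipient rate is 2/296 = 0.68.

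**The case against.** Reporting adverse events on everyone who entered follow-up is a declared and common choice, and it is not wrong in itself. The Section 5 sentence on PP can be read as promising a PP presentation of all data, which would make the gap one of incomplete shells.

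Much can also be recovered. The example listing carries treatment, Tables 14.3.2, 14.3.3 and 14.3.6 print patient IDs, Table 14.1.1 counts 202 patients discontinued as placebo, and Table 14.1.2 gives both population sizes. The outcomes most specific to the product are better protected: integration-site and RCR results are listed by patient, and the malignancy and biopsy questions are tabulated on PP. The analysis is descriptive, with no comparison between arms.

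The size is assumed throughout, and with few placebo entrants it is small. Protocol 1.1 mentions one further Phase II patient, but counting that patient as a recipient hardly changes the upper case: 38/75 = 0.51. It is also unclear whether placebo patients would enter the correlation in Table 14.3.5, because the text of 8.2.5 and the shell title describe different variables. Finally, changing the population now could break comparability with the 2016 interim analysis.

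These points limit the size and seriousness of the problem. They do not remove it. Section 8.2 names only the Safety denominator, and the index follows it. All study 202 IDs share one format that does not reveal the arm, so attribution means going back to the listings. No planned adverse-event percentage or rate describes 202 product recipients. Showing placebo in its own column lets the pooled counts be recovered by addition, which keeps the link to 2016.

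**Conclusion.** The concern holds. Followed as written, the plan gives 202 and Overall adverse-event percentages, and an 8.2.4 rate, that mix exposed and unexposed patients. The defect is pooling the arms with neither a treatment-received split nor a PP repeat. Using a Safety population is not the fault.

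For events confined to product recipients, the percentages can be understated by anything from about a tenth to a half in the 202 column, depending on how many placebo patients entered. The rate is less affected because placebo patients left early, and the direction of its error is not fixed. All sizes rest on assumed entrant numbers and follow-up times. The conclusion about which patients are counted does not. This should be fixed, but it does not undermine the data collected.

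**What to change.** 1. In SAP 8.2 and Tables 14.3.1 to 14.3.6, build the 202, 102/202 and Overall columns, and the patient-years and events in 8.2.4, from gene-transfer recipients. The existing PP population already defines them.
2. Show 202 placebo events and deaths separately, with their own N and patient-years to discontinuation, as description and not as a formal control.
3. Reword Section 5 so that its statement about PP agrees with 8.2 and the table index.

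The cost is SAP wording and one extra column or table version. Treatment received is already collected and listed, so no new data are needed. The percentages for product recipients may look somewhat less favourable than the pooled ones.

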1. INTRODUCTION

1.1 Background[†]

OZ1 is a Moloney Murine Leukemia Virus based retroviral vector (LNL6) containing a gene that encodes an anti-HIV-1 ribozyme directed against the human immunodeficiency virus type 1 (HIV-1) regulatory gene *tat*.^{13,14,15} A Phase I study demonstrated that the introduction of OZ1 into CD34+ cells *ex vivo* is technically feasible and safe.¹ The international, multi-center, Phase II, randomized, double-blind trial, OTH/OZ1-INT-1, was initiated to investigate the safety and efficacy of OZ1-transduced autologous CD34+ cells in patients with HIV-1 infection.⁹ One patient was enrolled in a Phase II protocol comparing the retroviral vector alone (LNL6) and OZ1. In a protocol amendment, OTH/OZ1-INT-1 became a placebo-controlled trial. Of the 74 patients to be enrolled in the placebo controlled protocol, approximately half received a placebo and half OZ1. The primary efficacy end point is the difference in viral load between the two groups at weeks 47 and 48 post-infusion. Patients continue in the OTH/OZ1-INT-1 treatment interruption follow-on phase until week 100 post-infusion as long as the viral load remains below 100,000 copies/ml, the CD4+ cell count is greater than 150 cells/mm³ and there are no other reasons to recommence antiretroviral therapy. At the end of the OTH/OZ1-INT-1 study (week 100 post-infusion), patients are invited to enter this long term follow-up (LTFU) protocol.

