1.2 Rationale for Study[†]

Food and Drug Administration (FDA)/Center for Biologics Evaluation and Research (CBER) recommends a 15-year time-period for follow-up observations. However, CBER also recognizes that assessment of risk is a continuous process, and the nature and duration of follow up observations may be revised accordingly.⁴ This follow up protocol is to assess the long-term safety of OZ1/LNL6 gene transfer product in patients who were enrolled in the OTH/OZ1-INT-1 study. Based on the integrated safety analysis of observations up to 10 years in this LTFU study, up to 15 years with the same OZ1/LNL6 gene transfer product in 2 Phase 1 LTFU studies (OZ1-HV1-101 and OZ1-HV1-102), and published reports of adverse events observed with gene therapeutic products using the same type of retroviral vector,^{2,3,5,6,7,8,10,11,12} the sponsor has determined that the risk to OZ1/LNL6 gene transfer product to recipients beyond 10 years post-infusion is minimal. Accordingly, this long term follow up study will conclude by 30 November 2017. This completion date represents a minimum of 10 years follow up following the receipt of OZ1/LNL6-modified CD34+ cells.

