### 8.2.1. Overall Summary of Adverse Events

The following will be summarized:

- Number and percentage of patients with at least one SAE
- Number and percentage of patients with at least one related SAE
- Number and percentage of patients with at least one severe, related SAE
- Number and percentage of patients with at least one NSRAEs
- Number and percentage of patients with SAE leading to death

- Number of SAEs
- Number of related SAEs
- Number of severe related SAEs
- Number of NSRAEs
- Number of SAE/NSRAE leading to death

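### Adverse event percentages over everyone who entered follow-up are not risks to any stated time, and only related SAEs get a patient-year rate

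*SAP*

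**What the plan says.** SAP 8.2 fixes the denominator: "The denominator used for the calculation of percentages will be the number of patients in the Safety population for the respective long term follow-ups". SAP 4.1 defines the Safety population as "any patient who was enrolled in either of the OZ1-HV1-101, OZ1-HV1-102 or OZ1-HV1-202 studies and continued into the respective long term follow-up protocol", with no minimum follow-up and no condition on the product received. Tables 14.3.1 to 14.3.3 use this base for 101, 102, 202 and Overall. One entry in SAP 8.2.1, for example, is "Number and percentage of patients with at least one related SAE".

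Observation time is unequal by design and by loss:

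- Protocol 1.2 cites "up to 15 years with the same OZ1/LNL6 gene transfer product in 2 Phase 1 LTFU studies". For 202 it says "This completion date represents a minimum of 10 years follow up following the receipt of OZ1/LNL6-modified CD34+ cells".
- SAP 6.2 expects withdrawal, loss to follow-up and re-instatement.
- SAP 3.1 records that "patients who were identified as having been enrolled in the placebo arm were subsequently discontinued from the long term follow-up study 202". Protocol 1.1 says of the parent trial that "approximately half received a placebo and half OZ1".

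The general rule in SAP 5 is "Unless otherwise stated missing data will not be imputed".

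Three parts of the SAP do take account of who is being observed:

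- SAP 8.2.4 and Table 14.3.4 divide the number of related SAEs by observed patient-years, counted from year 2 to the last safety assessment.
- SAP 8.5 reports clinical history, including new malignancies, over patients with information at each visit.
- SAP 8.2.5 counts patients on study and with an SAE by timepoint.

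**The concern.** A patient observed for one year and a patient observed for thirteen carry the same weight in the denominator. If the first leaves with no recorded event, the unobserved years count as event-free. The percentage is then not a risk to year 5, year 10 or any other time. It mixes risk with length of observation.

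Two misreadings follow. Within a study, the percentage can understate cumulative risk, and the shortfall grows with loss. Between columns, studies with the same hazard can show different percentages.

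In 202 the largest documented group leaving early is the placebo arm, which was never exposed to the product. These patients stay in the Safety denominator, and the SAP's index lists every adverse event table on the Safety population. SAP 5 says that the Per-Protocol population (the product recipients) will be used for all data, but no recipient-only adverse event table is listed.

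This matters because the outcomes of interest, such as insertional oncogenesis, may come late, and the final tables are the last planned account of them.

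**Working it through.** The documents state no event rate, retention rate or sample size calculation, so there is no figure of the plan's own to reproduce. What follows is an illustration.

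**Inputs from the documents**

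- Long-term follow-up starts 2 years after infusion (SAP 8.2.4).
- 101/102 maximum: 15 − 2 = 13 years (Protocol 1.2).
- 202 to year 10: 10 − 2 = 8 years.
- 202 at study end: SAP 1.1 and 6.1 put the last year-10 visit at 13 February 2016, so the last infusion is inferred as February 2006. From then to 30 November 2017 is 11.8 years, and 11.8 − 2 = 9.8 years. An End-of-Study visit held earlier would shorten this slightly.

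**Assumptions**

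- Constant hazard λ of 1% per year.
- A fraction w lost uniformly over T years, unrelated to risk.

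**1. Effect of loss within a study**

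True risk = 1 − exp(−λT).

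Crude percentage = (1 − w)(1 − exp(−λT)) + w[1 − (1 − exp(−λT))/(λT)].

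For T = 8 the true risk is 1 − exp(−0.08) = 7.69%. The bracketed term for a lost patient is 1 − 0.07688/0.08 = 3.90%.

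| Lost | Calculation | Crude |
|---|---|---|
| 20% | 0.8 × 7.69 + 0.2 × 3.90 | 6.93% |
| 40% | 0.6 × 7.69 + 0.4 × 3.90 | 6.17% |

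The relative shortfalls are about 10% and 20%.

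**2. Equal hazard, unequal length, no loss**

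- 13 years: 1 − exp(−0.13) = 12.19%.
- 9.8 years: 1 − exp(−0.098) = 9.34%.
- Ratio: 12.19/9.34 = 1.31.

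This gives every 101/102 patient the maximum follow-up, so it is an upper illustration.

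**3. The direction is not fixed**

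Add uniform loss to the 13-year study only. Its term for a lost patient is 1 − 0.12190/0.13 = 6.23%.

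- 40% lost: 0.6 × 12.19 + 0.4 × 6.23 = 9.81%, close to 9.34%.
- 50% lost: 0.5 × 12.19 + 0.5 × 6.23 = 9.21%, below 9.34%. The order is reversed.

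**4. Placebo patients in the 202 denominator**

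Assume that half of the 202 entrants were on placebo, had the same hazard, and left 0.5 to 2 years into follow-up. The rest are followed for 8 years.

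- Left at 0.5 years: 0.5 × 7.69 + 0.5 × 0.50 = 4.1%.
- Left at 2 years: 0.5 × 7.69 + 0.5 × 1.98 = 4.8%.

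Product recipients alone would show 7.7%. The share of placebo patients who entered follow-up, and when they left, are not stated.

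**5. What a patient-year rate does**

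Under the same assumptions, expected events divided by observed patient-years equals λ, here 0.01 per year, for 8, 9.8 or 13 years and for any non-informative loss. SAP 8.2.4 does this for related SAEs.

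**6. Outcomes left uncovered**

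| Outcome | Patient-year rate | Cumulative risk |
|---|---|---|
| Related SAE | Yes (8.2.4) | No |
| SAE of any cause | No | No |
| Death of any cause | No | No |
| Non-serious related event | No | No |
| Malignancy judged unrelated | No; per-visit responses only (8.5) | No |

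Table 14.3.4 is itself on the Safety population, so placebo person-time enters the 202 rate.

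**The case against.** The strongest reply is that the SAP already handles exposure where attribution to the product matters most. SAP 8.2.4 gives related SAEs per patient-year by study, SAP 8.5 gives malignancy responses with visit-level denominators, and SAP 6.2 and the listings show who left and when. This stands, and it narrows the gap to the outcomes without a rate. It does not close it. Protocol 10.2 makes malignancy (other than basal or squamous cell carcinoma) reportable regardless of causality, yet one judged unrelated falls outside the 8.2.4 rate. The 8.5 tables are per visit, neither cumulative nor split by study.

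The effect is also small in patients. Half of 74 is about 37 recipients. At 1% per year over 8 years, the shortfall with 20% to 40% loss is 0.3 to 0.6 of a patient (37 × 0.76% and 37 × 1.52%). At 5% per year with 40% loss it is about two (37 × (33.0% − 26.8%)). That stands too. The analysis is primarily descriptive (Protocol 9) and no between-study adverse event test is planned, so the harm is misreading rather than a false test result.

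A reader might infer more than the documents support:

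- **That everyone who leaves counts as event-free.** Events recorded before departure are counted. Telephone interviews, secondary contacts and re-entry (Protocol 7.1) recover some later ones.
- **That the longer studies must look more dangerous.** Step 3 shows that loss can cancel or reverse this.
- **That the distortion is 1.6-fold (12.2% against 7.7%).** That sets the 101/102 maximum against year 10 in 202, but final follow-up in 202 runs to November 2017.
- **That the denominator contradicts the no-imputation rule in SAP 5.** A crude proportion is not imputation. The difficulty is how it is read.

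**Conclusion.** The concern holds in a limited form. The percentages in Tables 14.3.1 to 14.3.3 are crude proportions over unequal observation. They can understate risk and should not be compared across columns. For all-cause SAEs, deaths, non-serious related events and malignancies judged unrelated, the SAP offers no person-time or cumulative summary to set beside them. No listed adverse event table is confined to product recipients.

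Under the stated assumptions the understatement is about 10% to 20% relative for 20% to 40% loss, and the between-study artefact is about 1.3-fold at most follow-up contrast with no loss. Hazard, loss and placebo exit times are all assumed. The 9.8 years is inferred from the visit schedule.

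It would be wrong to conclude that these percentages led the sponsor to its judgement of minimal risk. Protocol 1.2 limits that judgement to the period beyond 10 years after infusion and rests it on an integrated safety analysis and published reports. Amendment 4 is dated June 2017, before the final analysis expected in 2018. The documents do not say which adverse event summaries the integrated analysis used.

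**What to change.** 1. Extend the rate in SAP 8.2.4 and Table 14.3.4, with 95% confidence intervals, to all SAEs, deaths, non-serious related events and malignancies regardless of causality. State the malignancy definition, since Protocol 10.2 and the clinical history question treat skin cancers differently.
2. Present these for product recipients (the Per-Protocol population), and show the 202 placebo patients and their person-time separately.
3. In Table 14.3.1, show patient-years beside each percentage. Label the percentages as crude and not for comparison between columns.
4. Add cumulative incidence at 5 and 10 years after infusion, with numbers at risk, for first malignancy (death as competing event) and for death. Take entry at the start of long-term follow-up and censor at the last safety contact. Restrict this to 102/202 combined and overall, because study 101 appears from its table shells to be too small for a curve of its own.

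The cost is SAP wording and one or two added tables. The infusion and last-assessment dates are already used in SAP 6.4 and 8.2.4, and SAEs of any cause are recorded in the case report form. The downside is wide intervals at late years, which shows how little the data can say there.
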